**PARTNERS HUMAN RESEARCH COMMITTEE
DETAILED PROTOCOL**

PRINCIPAL/OVERALL INVESTIGATOR

[name].

PROTOCOL TITLE

A Randomized Controlled Trial of an Advanced Care Planning Video Decision Support Tool for Patients with End-Stage Liver Disease (Clinicaltrials.gov Identifier NCT03557086)

FUNDING

NIH-NIDDK National Institute of Diabetes and Digestive and Kidney Diseases
4K24DK078772-10

VERSION DATE

Version 9: February 6, 2020

A Randomized Controlled Trial of an Advanced Care Planning Video Decision Support Tool for Patients with End-Stage Liver Disease

Version 9: February 6, 2020

SPECIFIC AIMS

The goal of this pilot randomized trial is to assess the feasibility and preliminary efficacy of an advanced care planning (ACP) video decision support tool for improving patients' knowledge regarding their goals of care options and end of life (EOL) decision-making in patients with end-stage liver disease (ESLD).

Aim 1: To assess the feasibility and acceptability of an ACP video decision support tool for patients with ESLD

- *Hypothesis 1: The intervention will be deemed feasible and acceptable if at least 60% of eligible patients are enrolled in the study and if at least 60% of patients randomly assigned to the video intervention report that the video is acceptable*

Aim 2: To assess the impact of an ACP video decision support tool on patients' knowledge about their EOL care options

- *Hypothesis 2: Patients randomly assigned to the video intervention will report improved knowledge of their EOL care options compared to those randomized to the verbal narrative control*

Aim 3: To assess the impact of an ACP video decision support tool on patients' preferences for EOL care

- *Hypothesis 3: Patients randomly assigned to the ACP video will be more likely to prefer comfort care compared to those randomized to the verbal narrative control arm*
- *Hypothesis 4: Patients randomly assigned to the video intervention will be more likely to forgo cardiopulmonary resuscitation (CPR) and intubation compared to those randomized to the verbal narrative control arm*

Aim 4: To assess the impact of an ACP video decision support tool on patients' documented EOL care preferences

- *Hypothesis 5: Patients randomly assigned to the video intervention will be more likely to have their code status documented in the electronic healthcare record compared to those randomized to the verbal narrative control arm*

BACKGROUND AND SIGNIFICANCE

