Our proposed project is a single-center randomized controlled trial to assess the feasibility, acceptability and preliminary efficacy of an ACP video decision support tool versus a verbal narrative alone on EOL care preferences in transplant ineligible patients with ESLD in the outpatient setting. We will recruit up to 70 consecutive patients with ESLD who receive ambulatory care at the MGH Liver Center for this study. Patients will be randomized in a 1:1 fashion (**Figure 1**). To ensure that patients in this sample received longitudinal care (ruling out

A Randomized Controlled Trial of an Advanced Care Planning Video Decision Support Tool for Patients with End-Stage Liver Disease

Version 9: February 6, 2020

those being seen for second-opinion consultation), we will only include those patients who have had two or more visits to the MGH Liver Center.

Eligibility Criteria

Our proposed project is a single-center randomized controlled trial to assess the feasibility, acceptability and preliminary efficacy of an ACP video decision support tool versus a verbal narrative alone on EOL care preferences in transplant ineligible patients with ESLD. We will recruit up to 70 consecutive adult patients with ESLD who receive care at MGH for this study. Patients will be randomized in a 1:1 fashion (see **Schema for further details**).

Eligibility Criteria

All patients with ESLD who are \geq 18 years of age seen at the Massachusetts General Hospital will be screened for study participation. Our study population is defined as patients with cirrhosis complicated by at least one of the following clinically-evident decompensating events: 1) ascites; 2) hepatic encephalopathy; or 3) history of gastroesophageal variceal hemorrhage - which portends a poor prognosis.⁴⁰ Only patients who are deemed ineligible for liver transplantation by either their primary hepatologist or the inpatient hepatology consult service attending will be eligible for this study as this is a patient population for whom the diagnosis of ESLD is a terminal one.

Patients Inclusion Criteria:

[figure not shown]
1. \geq 18 years of age with an established diagnosis of ESLD
2. Patient must have either 1) primary hepatologist at the MGH Liver Center or an MGH-affiliated primary care physician, or 2) a previous inpatient admission at MGH
3. Deemed ineligible for liver transplantation as determined by the primary hepatologist or the inpatient hepatology consult service attending

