4. Ability to communicate in English and provide informed consent
5. A score \geq 7 on the Short Portable Mental Status Questionnaire⁴¹ (**Appendix A**)

Patients Exclusion Criteria:

1. Severe hepatic encephalopathy which the primary hepatologist or the inpatient hepatology consult service attending believes prohibits informed consent or participation in the study
2. Significant uncontrolled psychiatric disorders (psychotic disorder, bipolar disorder, major depression) or other co-morbid disease (dementia, cognitive impairment), which the primary hepatologist believes prohibits informed consent or participation in the study
3. Prior history of liver transplantation
4. Patient has been referred to or enrolled in hospice care
5. Patient has been referred to palliative care

We have limited enrollment to patients able to comprehend English, as the video is only available in English at this time. If the intervention is effective in improving advance care planning and the delivery of EOL care for patients with ESLD, we will develop videos in additional languages for future trials.

Figure 1

Once a potentially eligible patient is identified, the RA will send an email to the primary hepatologist in the outpatient setting, or the medicine attending and responding clinician in the inpatient setting (as well as the hepatology consult service if available) to notify them that their patient is eligible for study participation and inquire about any concerns regarding their participation. If the clinicians have objections to their patients' participation in the study, we will document the reason and not approach those individuals. If the clinicians do not have objections to their patients' participation in the study, we will ask the attendings to introduce the study to the eligible patient to obtain permission for the study staff to approach the patient. After obtaining permission from the primary hepatologist, inpatient hepatology consult attending and/or medicine attending, the RA will review the consent form with potential participants which will detail the nature of the study procedures. When obtaining informed consent, the RA will describe the goal

A Randomized Controlled Trial of an Advanced Care Planning Video Decision Support Tool for Patients with End-Stage Liver Disease

Version 9: February 6, 2020

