- *CPR Preferences*: Patients will report their CPR preferences as follows: “Yes, attempt CPR”, “No, do not attempt CPR”, or “Not sure.” (**Appendix E**)
- *Intubation Preferences*: Patients will report their intubation preferences as follows: “Yes, attempt intubation”, “No, do not attempt intubation”, or “Not sure.” (**Appendix E**)
- *Knowledge Questionnaire*: We will assess patients’ knowledge of goals of care as in previous studies using 5 true/false questions and 1 multiple choice question, each worth 1 point, for a summary score of 0 to 6 (higher score reflects greater knowledge)^{45,47,48} (**Appendix F**)
- *Acceptability of the Video*: For the video intervention arm alone, we will administer 3-items assessing patients’ comfort with watching the video, whether they find the video helpful in their understanding of the EOL care options, and whether they would recommend it to others.⁴⁹ (**Appendix G**)

We will also obtain the following important covariates and outcomes:

- *Disease-related variables*: We will collect variables from the EHR at the time of enrollment, including the etiology of ESLD, presence of clinically-evident decompensating events (ascites, esophageal variceal bleed, hepatic encephalopathy, or multiple), Model of End-Stage Liver Disease Sodium (MELD-Na) score, reason for transplant ineligibility, and clinical comorbidities using the modified Charlson Comorbidity Index.⁵⁰
- *Code Status Documentation in the EMR*: The RA will review the EHR to collect whether clinicians’ documented patients’ code status in the EMR (yes: documented, no: not documented) 3 months after study enrollment.

Table 1: Data Collection Timeline

	Baseline	Post-intervention	3 months post-enrollment
Demographics	X		
Self-Reported Health Status	X		
EOL Care Preferences	X	X	
CPR Preferences	X	X	
Intubation Preferences	X	X	

Knowledge Questionnaire	X	X	
Comfort/Satisfaction with Video (Intervention group only)		X	
Disease-related variables	X		
Code status documentation			X

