We will randomize up to 70 patients with ESLD for this project. The primary endpoint of the study is feasibility. We chose the sample size of 70 patients based on the feasibility of completing the project during the proposed timeframe and the ability to assess the preliminary efficacy of the intervention. Consistent with the behavioral intervention literature, at least 20 patients are needed in each group in a pilot study to estimate a parameter.^{54,55} Therefore, the proposed sample size will provide us with preliminary data that can be utilized to determine the effect size and adequately power future randomized trials. This is a commonly utilized study design for pilot testing of behavioral interventions and is consistent with the National Institute of Health Stage Model for Intervention Development. While the feasibility of the intervention can be assessed using a single-arm design, preliminary efficacy is better assessed utilizing a control group as we are proposing in this trial.

A Randomized Controlled Trial of an Advanced Care Planning Video Decision Support Tool for Patients with End-Stage Liver Disease

Analysis Plan

We will report baseline demographic and clinical characteristics of all study participants using means and proportions to describe continuous and categorical variables, respectively. Because this is a pilot study, we will use conservative ($\alpha = 0.05$) and liberal ($\alpha = 0.20$) critical values to assess statistical significance between the two arms in this pilot study.

Aim 1: The primary endpoint of the proposed study is feasibility. The proposed video intervention will be deemed feasible if at least 60% (95% CI +/- 13.6%) of eligible patients are enrolled in the study and complete at least 60% of the intervention sessions. The proposed video intervention will be deemed acceptable if at least 75% of patients randomized to the intervention arm report satisfaction and comfort with the video.

Aim 2: Changes in knowledge scores from before and after the intervention will be compared between the two groups using two-sample t-tests.

Aim 3: Post-intervention EOL care preferences (life-prolonging care, limited medical care, and comfort care), CPR preferences, and intubation preferences will be compared between the two groups using Fisher's exact tests. The change in CPR and intubation preferences before and after the intervention within each group will be compared using McNemar tests.

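### Code status is read only at 3 months, with no baseline and no date rule, so entries made before the session count as documented and shrink the Aim 4 difference by an unmeasured factor

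*Combined protocol and SAP*

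**What the plan says.** Hypothesis 5 (Specific Aims, Aim 4) is that video patients will be "more likely to have their code status documented in the electronic healthcare record" than narrative patients. Study Measures defines the outcome as a yes/no item from chart review: "code status in the EMR (yes: documented, no: not documented) 3 months after study enrollment". Table 1 marks it in the 3-month column only.

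A chart review at baseline is already planned: "We will collect variables from the EHR at the time of enrollment". The variables listed are etiology, decompensating events, MELD-Na, reason for transplant ineligibility and comorbidity. Code status is not among them. No section asks for the date of the code status entry or says how to treat patients already documented. The Analysis Plan for Aim 4 is a two-group Fisher's exact test without adjustment.

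Two provisions bear on whether earlier entries exist. Inclusion criterion 2 can be met by "a previous inpatient admission at MGH", and the recruitment text has the research assistant contact "the medicine attending and responding clinician in the inpatient setting". In the other direction, exclusion criterion 5 reads "Patient has been referred to palliative care", and criterion 4 removes hospice patients.

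**The concern.** Aim 4 is about the tool's impact on documented preferences. An entry that was on file before the session cannot respond to the tool, yet under a yes/no reading at 3 months it counts the same as one the session prompted. The Background cites a series in which most hospitalized patients with cirrhosis were designated full code on admission, so code status can be set before any study contact.

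The Sample Size section wants the pilot to supply "preliminary data that can be utilized to determine the effect size and adequately power future randomized trials". With b unknown, a small Aim 4 difference could mean a weak video effect or many prior entries. The observed difference also could not be carried to a trial with a different inpatient share. Randomization is unstratified, so prior documentation may differ between arms by chance, and no one would see it.

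**Working it through.** The documents give no rate, effect size or power for Aim 4, so there is no figure of the plan's own to reproduce.

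**Inputs from the documents.** Up to 70 patients randomized 1:1, so 35 per arm. Fisher's exact test. The Analysis Plan sets alpha 0.05 and 0.20 as "critical values to assess statistical significance between the two arms in this pilot study". Sidedness is not stated; two-sided is assumed.

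**Assumed inputs.** Among patients with no earlier entry, new documentation by 3 months is pC = 20% (narrative) and pV = 50% (video). The share already documented, b, is set to 0, 10%, 28% and 40%. The 28% is borrowed from the advance-directive rate in the Background. That is a different document, so it is only an illustration. Earlier entries are assumed still to read yes at 3 months.

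**Dilution.** The rate as written in each arm is b + (1 − b)p, so the observed difference is (1 − b)(pV − pC).

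- b = 10%: 28.0% v 55.0%, a difference of 0.90 × 30 = 27 points
- b = 28%: 42.4% v 64.0%, a difference of 0.72 × 30 = 21.6 points
- b = 40%: 52.0% v 70.0%, a difference of 0.60 × 30 = 18 points

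**Power.** Exact enumeration of the two-sided Fisher test. The restricted comparison uses 35(1 − b) patients per arm, rounded, at 20% v 50%.

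| b | Restricted n per arm | As written, alpha 0.05 | Restricted, alpha 0.05 | As written, alpha 0.20 | Restricted, alpha 0.20 |
|---|---|---|---|---|---|
| 0 | 35 | 69% | 69% | 88% | 88% |
| 10% | 32 | 54% | 64% | 78% | 86% |
| 28% | 25 | 33% | 51% | 61% | 75% |
| 40% | 21 | 26% | 40% | 50% | 70% |

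The restricted column fixes the number undocumented. Letting it vary as Binomial(35, 1 − b) gives about 67%, 55% and 46% at alpha 0.05, so the fixed-count figures do not flatter the restricted comparison.

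**Smaller effect.** With 20% v 40% at b = 28%, power as written v restricted is 15% v 23% at alpha 0.05 and 37% v 49% at alpha 0.20.

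**Future trial.** By the pooled two-proportion formula (80% power, alpha 0.05), 20% v 50% needs 39 per arm. On the outcome as written the need is 52, 83 or 115 per arm at b = 10%, 28% or 40%. Enrolling enough to have 39 undocumented patients takes 39/(1 − b) = 44, 55 or 65 per arm.

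**Chance imbalance.** Unequal prior documentation moves the arm difference by 1.96 × √[b(1 − b)/35 × (0.8² + 0.5²)]. That is about ±14 points at b = 28% and ±15 at b = 40%. It is already inside the power figures above.

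**Type I error.** With both arms at pC = 20%, the actual size of the Fisher test stays at 2.5% to 2.8% (nominal 0.05) and 12% to 13% (nominal 0.20) for b from 0 to 70%. The test is not biased.

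**The case against.** The strongest reply is that the outcome matches Hypothesis 5 as worded. The hypothesis speaks of code status being documented, not newly documented, and any documentation at 3 months in all randomized patients is a valid intention-to-treat comparison. That stands as far as validity goes. It does not answer the point about effect size, because Aim 4 asks for the tool's impact and the pilot is meant to inform later trials.

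The definition could also be read as documentation arising during the 3 months. The text does not say so, and under that reading a dated entry would still be needed to apply it. The exact factor (1 − b) does depend on earlier entries still reading yes.

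The size is wholly assumed. No section gives the inpatient share or any code status rate, and excluding hospice and palliative care referrals may lower b. All of this stands.

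The consent description mentions asking about prior advance care planning discussions. That is patient-reported, is not a chart code status, and appears in neither Table 1 nor the questionnaires in Appendices D to F.

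A simpler remedy is to keep all 70 patients and count only post-session entries. Under the same assumptions this gives power of 61%, 45% and 35% at alpha 0.05 for b = 10%, 28% and 40%. That is better than the plan, but below the restricted comparison (64%, 51%, 40%), and the difference stays diluted, though by a known factor.

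**Conclusion.** The concern holds. Followed as written, the plan scores pre-session entries as successes in both arms and collects nothing from which b could be estimated. Under the assumed 20% v 50%, power at alpha 0.05 is lower than in the restricted comparison by 10 points at b = 10%, 18 at b = 28% and 14 at b = 40%. The loss vanishes at b = 0, and the true b is unknown.

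This costs effect size, power and interpretability; it does not create false positives. Aim 4 is neither the primary outcome nor among the listed secondary outcomes, so the feasibility conclusion is untouched. The change should be made because it is cheap and Aim 4 has its own hypothesis and test. Confidence is medium, since the magnitude rests on assumed rates.

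**What to change.** 1. Add code status documentation (present or absent, with date of entry) to the enrollment chart review and to the baseline column of Table 1.
2. Define the Aim 4 outcome as first documentation dated after the study session and within 3 months.
3. Make the main comparison among patients with none at baseline. Stratifying the 3-month comparison by baseline documentation is equivalent. Baseline status is fixed before randomization, so the restriction preserves the randomized comparison.
4. Report b by arm.
5. As supporting results, give any documentation at 3 months in all randomized patients, and changed entries among those already documented.

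The cost is one dated field in a review already planned. For patients already enrolled it may be recoverable if chart entries carry dates. The downside is a smaller main Aim 4 set: about 32, 25 or 21 per arm at b = 10%, 28% or 40%. It falls below the 20 per group that the Sample Size section asks for only if 35(1 − b) < 20, that is, if b exceeds about 43%.

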We will collect and enter all patient data electronically using Research Electronic Data Capture (REDCap). The REDCap Survey is a tool for building and managing online surveys. Vanderbilt University, in collaboration with a consortium of institutional partners, has developed this software and workflow methodology for electronic collection and management of research and clinical trial data. Our research team has extensive experience using REDCap and will create and design the surveys in a web browser, with institutional information technology support. The REDCap Survey system offers secure, HIPAA compliant, web-based applications that provide an intuitive interface for participants to enter data, with real-time validation rules at the time of entry.

Participants will use tablet computers to complete questionnaires in clinic. If any participants refuse or are unable to complete the questionnaires on the computer, they will be permitted to use hard-copy paper versions. In addition, the patient data collected from the electronic health record will be abstracted throughout the study and directly inputted into REDCap.

Study Outcomes

- **Primary Outcome:** The primary outcome is feasibility. The proposed video intervention will be deemed feasible if at least 60% of eligible patients are enrolled in the study. The 60% feasibility cut-off is commonly used in behavioral intervention studies.⁵¹⁻⁵³
- **Secondary Outcomes:** The secondary outcomes will include patients' comfort/satisfaction with the video, patients' stated post-intervention EOL care preferences categorized as four options: Life-prolonging care, limited medical care, comfort care, or unsure; individual preferences for CPR and intubation before and after intervention in the verbal narrative and video groups; and change in knowledge scores after receiving the verbal narrative or video

Sample Size Calculation

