Aim 4: Code status documentation will be compared between the two groups using Fisher's exact tests.

Project Timeline	Table 1: Study Timeline and Study Procedures
Months 0-2	❖ Finalize protocol development and submit to Institutional Review Board for approval
Months 3-24	Data Collection ❖ Enroll up to 70 patients to participate in the prospective study ❖ Collect follow-up data on ACP documentation and prepare manuscript(s) for publication

REFERENCES

A Randomized Controlled Trial of an Advanced Care Planning Video Decision Support Tool for Patients with End-Stage Liver Disease

Version 9: February 6, 2020

8. Dying in America: improving quality and honoring individual preferences near the end of life. *Mil Med*. 2015;180(4):365-367.
10. Gillick MR. Advance care planning. *The New England journal of medicine*. 2004;350(1):7-8.

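### The ±13.6% precision given for the primary feasibility endpoint corresponds to 50 eligible patients, which is not a number in this design; 70 enrolled at 60% implies about 117 eligible and ±8.9%

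*Combined protocol and SAP*

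**What the plan says.** The primary endpoint is feasibility, measured as the proportion of eligible patients who enrol. Specific Aims (Hypothesis 1), Study Outcomes and Analysis Plan (Aim 1) all use the same denominator and the same 60% threshold; Study Outcomes puts it as "The proposed video intervention will be deemed feasible if at least 60% of eligible patients are enrolled in the study". Only the Analysis Plan attaches a precision: "at least 60% (95% CI +/- 13.6%) of eligible patients are enrolled in the study". It gives neither the number of patients behind the interval nor the method.

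On size, the Sample Size Calculation states "We will randomize up to 70 patients with ESLD for this project", and the Project Timeline repeats the ceiling: "Enroll up to 70 patients to participate in the prospective study". Allocation is 1:1. The same section cites 20 patients per group as the minimum for a pilot and justifies 70 by timeframe and preliminary efficacy, not by precision. No expected number of eligible patients is given.

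On who counts as eligible, Study Design and Schema places the trial in the outpatient setting and says "we will only include those patients who have had two or more visits to the MGH Liver Center". Item 2 of the inclusion criteria instead accepts a patient with a "primary hepatologist at the MGH Liver Center or an MGH-affiliated primary care physician, or 2) a previous inpatient admission at MGH". The recruitment procedure after the exclusion criteria also covers inpatients.

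**The concern.** A half-width for a proportion is fixed by the proportion, the confidence level and the denominator. Two of these are stated (60% and 95%), so the third can be recovered and compared with the design. The recovered value matches neither the planned enrolment nor the number of eligible patients which that enrolment implies.

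This is the protocol's only statement of how precisely the primary endpoint will be estimated. A reader would take from it that an observed 60% is compatible with anything from 46.4% to 73.6%, which is not what a trial of this size would deliver.

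The conflicting eligibility texts add to the problem. A patient with a prior admission and no Liver Center visits is in the denominator under one text and outside it under the other. The percentage set against 60% is therefore not uniquely determined.

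**Working it through.** **Inputs**
- Proportion p = 0.60 and stated half-width 0.136 at 95%: Analysis Plan, Aim 1.
- Denominator, eligible patients: Specific Aims, Study Outcomes, Analysis Plan.
- Planned enrolment, up to 70, allocated 1:1 (35 per arm at 70): Sample Size Calculation, Study Design and Schema, Project Timeline.
- Pilot minimum, 20 per group (40 in total): Sample Size Calculation.
- Assumption: a two-sided Wald interval, because the protocol names no method.

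**Step 1. Reproduce the plan's figure.** Half-width h = 1.96 × √(p(1 − p)/n). Solving for n:

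n = 0.24 × (1.96/0.136)² = 49.8.

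At n = 50, h = 1.96 × √(0.24/50) = 13.58 points, which rounds to 13.6. At n = 49 it is 13.72 and at n = 51 it is 13.45, so 50 is the only whole number that gives the printed value.

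**Step 2. Find the denominator the design implies.** With 70 enrolled at exactly 60%, eligible = 70/0.60 = 116.7, about 117.

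h = 1.96 × √(0.24/117) = 8.88 points, giving 60 ± 8.9, or about 51% to 69%. The exact (Clopper-Pearson) interval for 70/117 is 50.4% to 68.8%.

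**Step 3. Try every other number the design offers.**

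| Denominator | Where it comes from | Half-width (points) |
|---|---|---|
| 117 | eligible, if 70 enrol at 60% | 8.9 |
| 70 | enrolled count used in error as denominator | 11.5 |
| 67 | eligible, if 40 enrol at 60% (40/0.60 = 66.7) | 11.7 |
| 40 | pilot minimum used in error as denominator | 15.2 |
| 35 | one arm | 16.2 |

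None gives 13.6.

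**Step 4. Try other methods.** At 95%, Wilson and Agresti-Coull intervals need n = 46 to give 13.6, a Wald interval at p = 0.5 needs 52, Clopper-Pearson about 54, and a continuity-corrected interval 57. None of these is a design number. A 90% interval on 35 patients does give 13.6, but it contradicts both the stated 95% level and the eligible-patient denominator.

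**Step 5. Ask whether 50 could belong to the design.** If 50 were eligible, 60% would be 30 enrolled, or 15 per arm, below the plan's own minimum of 20. If 50 were the number enrolled, about 83 would be eligible (50/0.60 = 83.3) and the half-width would be 10.5.

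**Step 6. Size of the discrepancy.** 13.6/8.88 = 1.53, so the stated half-width is about 53% too large at full enrolment. Against the 40-patient minimum, 13.6/11.73 = 1.16, about 16% too large.

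**Step 7. Sensitivity to who is counted.** With 70 enrolled, 70/116 = 60.3% meets the threshold and 70/117 = 59.8% does not. Near 60%, one non-enrolled patient counted as eligible or not decides the result. The documents give no basis for estimating how many patients the two eligibility texts would classify differently.

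**The case against.** The strongest reply is that 70 is a ceiling and no eligible count is stated, so 8.9 holds only at full enrolment and exactly 60%. At the plan's minimum of 40 enrolled the value is 11.7, and a fair range is 8.9 to 11.7. This stands as a qualification: 8.9 must be printed with its condition. It does not rescue 13.6, which lies outside that range. Nor is 70 an arbitrary choice, since the Sample Size Calculation names it as the chosen sample size.

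A second reply is that the method is unnamed, so 50 rests on a Wald assumption. That is true, but the other 95% methods tried point to 46 to 57, which are equally absent from the design.

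A third is that little turns on the figure. The rule is a point threshold, 70 was not derived from precision, and the error understates precision, so it does not flatter the trial. All of this is correct. It limits how serious the matter is but does not make the number right.

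Finally, the eligibility conflict is a different kind of problem and does not explain 13.6, and the numbered criteria together with the inpatient procedure suggest that the two-visit sentence may be a leftover. That may be so, but the sentence stands in the current text. It bears on the same denominator, so the two points are best corrected together.

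**Conclusion.** The concern holds. The stated ±13.6% cannot be reproduced from the design. It corresponds to 50 eligible patients under a 95% Wald interval at 60%, and the documents do not show where 50 comes from. At the planned 70 enrolled and exactly 60%, the value is ±8.9% on about 117 eligible; at the 20-per-group minimum it is ±11.7%. Separately, the two eligibility descriptions leave the denominator of the primary endpoint without a single definition. Both should be corrected, although the interval figure by itself changes no sample size and no pass/fail decision.

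**What to change.** In Analysis Plan, Aim 1, replace the ±13.6% with ±8.9%, stating its basis (70 enrolled of about 117 eligible at 60%) and the interval method. Add a sentence saying that the reported interval will be computed on the actual number of eligible patients.

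Reconcile the outpatient, two-visit sentence in Study Design and Schema with inclusion criterion 2 and the inpatient recruitment procedure, so that one definition of eligible sets the denominator. Which definition applies is for the sponsor to decide.

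The cost is one figure, one added sentence and one reconciled eligibility statement. No additional patients or data are needed.
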